Although the incidence of endophthalmitis has been reported to be less than 0.25% (range 0.02% to 0.25%);¹⁻⁹ its consequences can be devastating. To prevent endophthalmitis, the use of prophylactic antibiotics has become the standard of care.¹⁰⁻¹² The type of prevention used varies from surgeon to surgeon and from Country to Country. Some surgeons prefer to use topical drops, others intracameral antibiotics, and some others rather use subconjunctival injections. Factors that could influence the ophthalmologist's selection include antibiotic spectrum, efficacy, side effects, cost, and experience, among others. Chang et al¹¹ reported that 91 % of American Society of Cataract and Refractive Surgery members used prophylactic antibiotics starting prior to surgery and 98% used them postoperatively. The use of intracameral antibiotics alone or in conjunction with the topical one has shown to further reduce the incidence of endophthalmitis.^{3, 9, 13}

The incidence of pseudophakic cystoid macular edema (CME) has been reported from 0.1% up to 4% and it depends on the method used to diagnose it. The incidence of angiographic CME is higher (up to 70%) than the incidence of clinically significant CME.^{14, 15} There are different factors that affect its incidence: type of surgery,¹⁵ presence of predisposing conditions such as intraocular inflammation (i.e. uveitis)^{16, 17} and systemic diseases (i.e. diabetes).¹⁸

Several studies have shown the effectiveness of steroids and NSAIDs in the prevention of CME after cataract surgery not just in diabetic patients. Furthermore, some studies have shown a greater reduction in the incidence of CME when using NSAIDs compared to steroid alone.¹⁹⁻²¹

Even though, the large body of literature that supports the significance of prophylactic eye drops prior to surgery, patient compliance is a common problem. Different factors have been associated with patient's lack of compliance. It could be due to patient's inability to self-

administer the drops, lack of understanding of the importance of using the prophylactic treatment as well as understanding the instructions of how to administer the drops and its storage,²² or just forgetfulness or the fact that they don't like to put the drops multiple times a day for 2-4 weeks, therefore they just avoid doing it. About 64% of patients adhere to the prescribed treatment.^{23, 24}

There is a new alternative that combines the most commonly used antibiotic and anti-inflammatories into a single drop. The use of a single drop compounded ophthalmic solution may offer advantages such as increased compliance, patient comfort and reduced ocular toxicity. Three combinations are available today: Pred-Gati, Prednisolone acetate and gatifloxacin hydrochloride; Pred-Nepaf, Prednisolone acetate and nepafenac; and Pred-Gati-Nepaf, Prednisolone acetate, gatifloxacin hydrochloride, and nepafenac. Different studies have shown the safety and efficacy of topical antibiotic/steroid combination with comparable results to standard single component topical medication used prophylactically pre and post cataract surgery.²⁵⁻²⁸ Additionally, in a recent study, Pred-Moxi-Ketor used three times a day for one week followed by Pred-Ketor twice a day for 2 – 4 weeks was compared to an intravitreal injection containing triamcinolone, moxifloxacin and vancomycin (Tri-Moxi-Vanc). Results showed similar outcomes with good control of postoperative inflammation and patient comfort without any unexpected adverse events.²⁹

The purpose of this study is to evaluate the efficacy of Pred-Gati-Brom and compare it to the standard topical drops regimen used for routine cataract surgery.

1. OBJECTIVE:

To assess the efficacy of a formulation containing prednisolone acetate, gatifloxacin hydrochloride, and bromfenac used as combination drop therapy before and after routine cataract surgery and intraocular (IOL) implantation compared to standard prophylactic treatment that includes the topical use of Gatifloxacin, Bromfenac, and Prednisolone acetate 1%.

2. STUDY DESIGN AND METHODS:

2.1. Assessed article: Formulation containing prednisolone acetate, gatifloxacin hydrochloride, and bromfenac.

2.2. Study Design: Prospective, randomized, single site, contralateral eye study.

2.3. Subjects:

2.3.1. Inclusion Criteria:

Subjects **MUST** fulfill the following conditions to qualify for enrollment into the trial

1. Subject is undergoing bilateral cataract extraction or refractive lens exchange with intraocular lens implantation.
2. Gender: both males and females.
3. Age: 50 years and older.
4. Willing and able to provide written informed consent for participation in the study.
5. Willing and able to comply with scheduled visits and other study procedures.
6. Willing and able to administer eye drops and record the times the drops were instilled.
7. Scheduled to undergo standard cataract surgery with topical anesthesia in both eyes within 6-15 days between surgeries.
8. Potential postoperative best-corrected visual acuity of 20/30 or better.

2.3.2. Exclusion Criteria:

Subjects with **ANY** of the following conditions on the eligibility exam may **NOT** be enrolled into the trial.

1. Severe preoperative ocular pathology: amblyopia, rubella cataract, proliferative diabetic retinopathy, shallow anterior chamber, macular edema, aniridia or iris atrophy, uveitis, history of iritis, iris neovascularization, medically uncontrolled glaucoma, microphthalmos or macrophthalmos, optic nerve atrophy, advanced macular degeneration, advanced glaucomatous damage, etc.
2. Uncontrolled diabetes.
3. Use of any systemic or topical drug known to interfere with visual performance.
4. Contact lens use during the active treatment portion of the trial.
5. Any concurrent infectious/noninfectious conjunctivitis, keratitis or uveitis.
6. History of chronic intraocular inflammation.
7. History of retinal detachment.
8. Pseudoexfoliation syndrome or any other condition that has the potential to weaken the zonules.
9. Any additional ocular surgical procedures at time of cataract extraction (i.e. iStent) except corneal incisions for the correction of astigmatism.
10. Anesthesia other than topical anesthesia (i.e. retrobulbar, general, etc).
11. Any clinically significant, serious or severe medical or psychiatric condition that may increase the risk associated with study participation or may interfere with the interpretation of study results.
12. Participation in (or current participation) any ophthalmic investigational drug or device trial within the previous 30 days prior to the start date of this trial.
13. Intraocular conventional surgery within the past three months or intraocular laser surgery within one month.

The principal investigator reserves the right to declare a patient ineligible or non-evaluable based on medical evidence that indicates the patient is unsuitable for the trial.

3.1. Informed Consent / Subject enrollment

No subject will be enrolled into the study that does not meet the inclusion/exclusion criteria and does not sign the current approved informed consent document. Informed consent will be obtained prior to collecting any data for the study. The original signed documents will be maintained by the investigator as a permanent part of the subject's medical records. A signed copy will be provided to the subject.

3.2. Surgery Procedures:

Eyes of the study participants will be randomly assigned to one of two groups:

- Group A, test eye: Combination Drop Therapy (Pred-Gati-Brom)
The combination drop therapy containing prednisolone acetate 1%, gatifloxacin 0.5%, and bromfenac 0.075% used three times a day (TID) starting 1 day prior to surgery and continuing after surgery for 2 weeks then twice a day for a week and once a day for another week.
- Group B, control eye:
 - Gatifloxacin 0.5%, 1 drop, QID for 3 days prior to surgery and will continue for 2 weeks after surgery and then discontinue.
 - Bromfenac 0.09%: 1 drop TID starting 3 days before surgery and TID for 2 weeks after surgery, tapered to BID for 2 weeks, and then discontinued.
 - Prednisolone acetate 1% will be started after surgery QID for 2 weeks, tapered to BID for 2 weeks, and then discontinued.

Additional Preoperative/Intraoperative Medications:

- a. Routine medications including OVD, intracameral antibiotic (same to be used in both eyes), etc.

The use of antibiotics in the bottle is not allowed.

3.3. Study Visit Schedule and Assessments (Table 1).

3.3.1. Visit Schedule: Subjects will be examined at the following intervals:

1. Visit 1: Screening and enrollment: Preoperative evaluation completed not more than eight weeks before surgery

2. Visit 2: Day of Surgery
3. Visit 3: Day 1
3. Visit 4: Day 15 \pm 2 days postoperative after second eye surgery
4. Visit 5: Month 1: 30 \pm 5 days postoperative after second eye surgery

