3.3.2. Measurements and evaluations

1. Visit 1: Informed consent process will be conducted at this visit. Assessments include uncorrected and best-corrected ETDRS visual acuity at 4 m (UCVA / BCVA), manifest refraction, intraocular pressure (IOP) using Goldman tonometer, and slit lamp examination including dilated fundus exam, cataract density and type, ultrasonic central corneal pachymetry (UCCP), and optical coherence tomography (OCT). Symptoms (foreign body sensation (FBS) and burning/stinging) and pain in each eye will be assessed and compared with that of the fellow eye. Any testing that is part of the site's standard of care preoperative cataract surgery evaluation may be performed prior to the informed consent being signed provided these tests are conducted within 90 days of the surgery and notation of the date performed is entered onto the source document.

The first eye undergoing surgery will be randomized to either Group A (test) or Group B (control). Randomization will ensure that an equal number of first eyes are test and control.

2. Visit 2: The surgeon may use his preferred cataract extraction technique (manual or laser). The lens will be implanted in the bag. The following information will be captured the day of surgery: phaco technique (manual or laser), phacoemulsification time, cumulative dissipated energy (CDE), estimated fluid used, and duration of surgery (from opening/creating the incision to hydration of the wound).
3. Visit 3: Slit lamp examination, UCVA, IOP, UCCP, patient satisfaction, symptoms and pain will be assessed.
4. Visit 4 and 5: Slit lamp examination, UCVA, BCVA, IOP, UCCP, OCT, patient satisfaction, symptoms and pain will be assessed as well as presence of rebound inflammation. Rebound inflammation will be diagnosed based on the following symptoms: ocular pain, blurry vision, light sensitivity and redness; and slit lamp examination showing anterior chamber cells and/or flare. Rebound inflammation will be treated with Prednisolone acetate 1% to QID for 2 days, continued BID for a week and QD for one additional week then discontinued.

All adverse events and complaints will be monitored and recorded at all study visits.

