Appendix 1 summarizes the standard evaluation procedures.

Table 1. Visits and Study Assessments

Study Assessments	Visit 1 Preoperative	Visit 2 Operative	Visit 3 Day 1	Visit 4 Day 15 ±2	Visit 5 Day 30 ±5
Inclusion/Exclusion Criteria	x				
Consent Subject	x				
Patient demographics (age, gender, race, ethnicity)	x				
Manifest Refraction	x		x	x	x
UCDVA	x		x	x	x
BCDVA	x			x	x
Goldman Tonometry (IOP)	x		x	x	x
Complete slit lamp exam	x		x	x	x
Dilated fundus exam	x				†
Cataract density	x				
Ultrasonic central corneal pachymetry	x		x	x	x
Central macular thickness (OCT)	x			x	x
Use of femtosecond laser		x			
Phacoemulsification time		x			
CDE		x			
Estimated fluid used		x			
Duration of surgery		x			
Record Lens Model Implanted		x			
Patient satisfaction					x
Symptoms (FBS & burning/stinging)	x		x	x	x

Pain	x		x	x	x
Adverse events / device deficiency		x	x	x	x

x To be performed as scheduled

† To be performed as deemed necessary by the investigator.

4. Study Completion Criteria

- 4.1. Patient Completion of Study: If a study patient has completed the final visit (Visit 5) of the study, he/she is considered to have completed the study.
- 4.2. Patient Discontinuation/Withdrawal: Each study patient may voluntarily discontinue the study at any time they choose. Study patients who cannot complete the study for administrative reasons (e.g., non-compliance, failure to meet visit schedule, etc.) will be discontinued from the study. Study patients discontinued during the enrollment phase (prior to surgery) of the study will be replaced.
- 4.3. Patient Termination: A study patient will be terminated if the study patient develops any severe adverse event that may be related to the study. A study patient will receive appropriate treatment at the discretion of the investigator. Notification of termination will be clearly documented. These study patients are considered to have completed the study and will not be replaced.
- 4.4. Study Termination: The investigator with appropriate notification may terminate the study. If, after clinical observations, the investigator feels that it may be unwise to continue the study, he may stop the study.
- 4.5. Study Completion: The study will be complete when all enrolled patients have completed Visit 5 or have been terminated from the study.

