5. STATISTICAL CONSIDERATIONS

5.1. Sample size

We estimate that the ability of the Cirrus OCT to measure changes in macular thickness has a standard deviation around 6 microns. For sample size calculation we set the statistical significance to $\alpha = 0.05$ with a power (beta) of 0.9. Using a dependent model, detecting a 5 micron difference in the change in retinal thickness between eyes is estimated to require 30 subjects. To allow for 15% dropout, 35 subjects will be enrolled.

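### Visits 4 and 5 are timed only from second-eye surgery, so first eyes never meet the Day 15 endpoint and rarely the Day 30 one, and the analysis plan does not use the randomised treatment order

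*Combined protocol and SAP*

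**What the plan says.** Inclusion criterion 7 (section 2.3.1) requires patients to be "Scheduled to undergo standard cataract surgery with topical anesthesia in both eyes within 6-15 days between surgeries". Section 3.3.1 times Visit 4 at Day 15 ± "2 days postoperative after second eye surgery" and Visit 5 at Day 30 ± 5 from the same anchor. No Day 15 or Day 30 visit counted from first-eye surgery is listed, and Table 1 places post-operative OCT only at these two visits.

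The labels elsewhere do not carry the anchor. Table 1 heads the column "Visit 4 Day 15 ±2", section 5.3.1 defines the primary endpoint as change in macular thickness at Days 15 ± 2 and 30 ± 5, and Appendix 1 item 5 refers to days 15 and 30.

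Under section 3.2 the test drop runs for 2 weeks after surgery, "then twice a day for a week and once a day for another week". In the control eye bromfenac is given "TID for 2 weeks after surgery, tapered to BID for 2 weeks, and then discontinued", and prednisolone also runs for 2 + 2 weeks. Both courses therefore last 28 post-operative days.

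On allocation, section 3.3.2 states: "The first eye undergoing surgery will be randomized to either Group A (test) or Group B (control"), and "Randomization will ensure that an equal number of first eyes are test and control". Section 5.2 names no primary test and does not mention order, pairing or days since surgery. Section 5.1 refers to a dependent model, but only for the sample size.

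**The concern.** In a contralateral-eye trial each patient serves as their own control, so the two eyes should be compared like for like or the difference between them handled in the analysis. Here the eyes are always 6-15 days apart in recovery at the visits that supply the primary endpoint, and sometimes one eye has finished its drops while the other has not.

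Two things are at stake. First, the endpoint definition: a result reported as a Day 15 effect would describe that day for no first eye, which is half of all eyes analysed. Second, efficiency: if macular thickness change depends on time since surgery, an analysis that ignores order treats this systematic difference as noise.

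**Working it through.** **Timing.** Inputs: lag between surgeries 6-15 days (2.3.1); visit windows 13-17 and 25-35 days after second-eye surgery (3.3.1). First-eye day = second-eye day + lag.

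- Visit 4: first eye from 13 + 6 = 19 to 17 + 15 = 32. There are 5 days × 10 lags = 50 combinations. The first eye is within 13-17 in 0 of 50. It is within 25-35, the plan's own Day 30 window, in 4 + 5 + 6 + 7 + 8 = 30 of 50.
- Visit 5: first eye from 25 + 6 = 31 to 35 + 15 = 50. There are 11 × 10 = 110 combinations. The first eye is within 25-35 in 5 + 4 + 3 + 2 + 1 = 15 of 110.

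These counts weight combinations equally. They are not probabilities.

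**On or off treatment.** Both courses end after day 28, so this status can be compared across regimens.

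- Visit 4: the second eye (day 13-17) is always on drops. The first eye is past day 28 in 1 + 2 + 3 + 4 = 10 of 50 combinations.
- Visit 5: the first eye (day 31 or later) is always off. The second eye is still on drops at days 25-28, giving 4 × 10 = 40 of 110.

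**The plan's sample size.** Section 5.1 says that "detecting a 5 micron difference in the change in retinal thickness between eyes is estimated to require 30 subjects". With two-sided alpha 0.05 and power 0.9, n = (1.960 + 1.282)² × SD² / 5². If 6 microns is a per-eye SD and the eyes are uncorrelated, the paired SD is 6 × √2 = 8.49 and n = 30.3, which approximately reproduces 30. If 6 is already the paired SD, n = 15.1. Section 5.1 does not say which, so both are carried forward.

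**Bias.** Let τ be the treatment effect and d the first-minus-second-eye shift in thickness change. The test-minus-control difference has mean τ + d when the test eye goes first and τ − d when it goes second. With n1 and n2 patients per order, the plain mean estimates τ + d(n1 − n2)/(n1 + n2).

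- Equal split: the bias is 0.
- 35 enrolled, at best 18:17: d/35 = 0.03d.
- A hypothetical 17:13 split among 30 completers: 4d/30 = 0.13d, or 0.27, 0.40 and 0.67 micron at d = 2, 3 and 5.

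**Precision.** With a 15:15 split, the true standard error of the mean is SD/√30 whatever d is. The unadjusted test instead estimates a variance with expectation SD² + d² × 30/29, so it overstates the standard error. Simulation (400,000 runs per cell, 5 micron effect for power, assumed d):

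| d (microns) | 0 | 2 | 3 | 5 | 8 |
|---|---|---|---|---|---|
| SD 8.49, no order term: power % | 87.7 | 86.5 | 84.9 | 79.6 | 65.2 |
| type I error % | 5.0 | 4.4 | 3.8 | 2.3 | 0.8 |
| mean 95% CI half-width | 3.14 | 3.23 | 3.34 | 3.66 | 4.36 |
| SD 6, no order term: power % | 99.3 | 99.0 | 98.6 | 96.5 | 85.9 |
| type I error % | 5.0 | 3.9 | 2.9 | 1.1 | 0.1 |
| mean 95% CI half-width | 2.22 | 2.35 | 2.49 | 2.92 | 3.76 |

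With an order term and any constant d, power is 87.6% (SD 8.49) or 99.3% (SD 6), type I error is 5.0%, and the half-width is 3.14 or 2.22 microns. If the shift instead grows in proportion to the lag with a mean of 5 microns, power with and without the term is 86.8% and 78.7% (SD 8.49), or 99.0% and 95.8% (SD 6).

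**The case against.** The strongest reply is that the design already deals with the serious risk. A reader might infer that the comparison is confounded with time since surgery. The documents do not support that: treatment of the first-operated eye is randomised and balanced, so a constant shift cancels on average, and the residual bias from an uneven split is small beside the interval half-widths. This part of the reply stands.

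A reader might also infer a serious loss of power. That needs d of about 5-8 microns, as large as or larger than the 5 micron target difference, and the documents give no time course from which any d could be taken. This stands too.

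A third tempting step is to count how often fellow eyes sit on different taper steps by applying one taper to both eyes. Such pairs cannot occur, since one eye is always on the test regimen and the other on control. Only on/off status is used here.

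It can also be said that the anchor is stated openly in 3.3.1, that 5.2 does not forbid an order-adjusted model, and that scanning both eyes at the shared visits is inferred (Visits 2 and 3 are also listed once despite two surgeries). All true. But 5.3.1 attaches day windows to the primary endpoint without the anchor, no other post-operative OCT visit is scheduled, and leaving the model open allows the choice to be made after the data are seen.

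**Conclusion.** The point holds, and it rests mainly on the endpoint definition. As written, no first eye can meet the Day 15 ± 2 endpoint, and first eyes meet Day 30 ± 5 in only 15 of 110 equally weighted combinations. This needs no assumption about d, only the inference that both eyes are scanned at the shared visits.

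The analysis part is secondary: a loss of efficiency, not an invalid comparison. With 30 pairs split 15:15, omitting order costs about 1-3 power points at d = 2-3 microns and about 8 points at d = 5 if the paired SD is 8.49. If the paired SD is 6, the losses are under 1 point and about 3 points. The error is in the conservative direction. The values of d are assumed, and the SD depends on how section 5.1 is read.

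**What to change.** 1. **Section 5.2.** Prespecify that the primary analysis models each patient's test-minus-control difference in change from baseline, with treatment order (test eye operated first or second) as a factor, and that the treatment effect is the equally weighted mean of the two order-specific means. State what this estimates: the average of the treatment effects at the first-eye and second-eye post-operative times of that visit.

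2. **Sections 5.3.1 and 5.3.2, the Table 1 headings and Appendix 1.** Define these time points as Visit 4 and Visit 5, counted from second-eye surgery, and give the ranges: Visit 4, second eye day 13-17 and first eye day 19-32; Visit 5, second eye day 25-35 and first eye day 31-50. Results should not then be reported as Day 15 and Day 30 effects for both eyes.

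3. **Interpretation.** The visit schedule does not change, so the 6-15 day offset between eyes remains. State it as a limit on interpretation.

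The cost is text and one degree of freedom. If d = 0, power goes from 87.68% to 87.60% and the half-width from 3.141 to 3.145 microns at SD 8.49, and from 99.28% to 99.27% and 2.221 to 2.224 microns at SD 6. No visits, scans or patients are added, and treatment is untouched.

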3.3.2. Measurements and evaluations

1. Visit 1: Informed consent process will be conducted at this visit. Assessments include uncorrected and best-corrected ETDRS visual acuity at 4 m (UCVA / BCVA), manifest refraction, intraocular pressure (IOP) using Goldman tonometer, and slit lamp examination including dilated fundus exam, cataract density and type, ultrasonic central corneal pachymetry (UCCP), and optical coherence tomography (OCT). Symptoms (foreign body sensation (FBS) and burning/stinging) and pain in each eye will be assessed and compared with that of the fellow eye. Any testing that is part of the site's standard of care preoperative cataract surgery evaluation may be performed prior to the informed consent being signed provided these tests are conducted within 90 days of the surgery and notation of the date performed is entered onto the source document.

The first eye undergoing surgery will be randomized to either Group A (test) or Group B (control). Randomization will ensure that an equal number of first eyes are test and control.

2. Visit 2: The surgeon may use his preferred cataract extraction technique (manual or laser). The lens will be implanted in the bag. The following information will be captured the day of surgery: phaco technique (manual or laser), phacoemulsification time, cumulative dissipated energy (CDE), estimated fluid used, and duration of surgery (from opening/creating the incision to hydration of the wound).
3. Visit 3: Slit lamp examination, UCVA, IOP, UCCP, patient satisfaction, symptoms and pain will be assessed.
4. Visit 4 and 5: Slit lamp examination, UCVA, BCVA, IOP, UCCP, OCT, patient satisfaction, symptoms and pain will be assessed as well as presence of rebound inflammation. Rebound inflammation will be diagnosed based on the following symptoms: ocular pain, blurry vision, light sensitivity and redness; and slit lamp examination showing anterior chamber cells and/or flare. Rebound inflammation will be treated with Prednisolone acetate 1% to QID for 2 days, continued BID for a week and QD for one additional week then discontinued.

All adverse events and complaints will be monitored and recorded at all study visits.

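### In the second-operated eye, the last check for rebound inflammation may fall before the drops have stopped, and no later visit records what follows

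*Combined protocol and SAP*

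**What the plan says.** Section 3.3.2 lists rebound for Visits 4 and 5 only: "symptoms and pain will be assessed as well as presence of rebound inflammation". It is not listed for Day 1: "Visit 3: Slit lamp examination, UCVA, IOP, UCCP, patient satisfaction, symptoms and pain will be assessed". The diagnosis needs symptoms together with anterior chamber cells or flare, and it triggers a prednisolone course of 2 days, a week and a further week.

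Section 3.3.1 counts both visits from the second operation: "Visit 4: Day 15 \pm 2 days postoperative after second eye surgery" and "Visit 5: Month 1: 30 \pm 5 days postoperative after second eye surgery". Table 1 gives "Visit 5 Day 30 ±5" without saying which eye's surgery is meant, and Appendix 1 does not say either. Inclusion criterion 7 in 2.3.1 puts the two operations 6 to 15 days apart.

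In 3.2 the test eye takes the combination three times a day, "continuing after surgery for 2 weeks then twice a day for a week and once a day for another week". For the control eye, "Prednisolone acetate 1% will be started after surgery QID for 2 weeks, tapered to BID for 2 weeks, and then discontinued".

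Section 4.1 treats a patient as complete at Visit 5, and 4.5 closes the study on the same basis: "The study will be complete when all enrolled patients have completed Visit 5 or have been terminated from the study". Section 3.3.2 ties the recording of adverse events to study visits.

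**The concern.** Rebound after a steroid is stopped can be seen only once it has been stopped. If the last permitted examination comes while an eye is still on drops, a site that follows the protocol exactly can record no rebound in an eye that has not yet been at risk of it. If a case is found at the last visit, its treatment and outcome lie outside the study. Rebound has its own definition and treatment rule here, so readers will expect a usable count. The question is how many eyes are affected, and whether the loss falls more on one regimen.

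**Working it through.** **Inputs.** Post-operative drops (3.2): test eye 14 + 7 + 7 = 28 days; control eye 14 + 14 = 28 days. The last drop is Day 28, or Day 27 if the day of surgery is the first drop day. Highest-frequency dosing ends at about Day 14. Visit windows (3.3.1), counted from second-eye surgery: Visit 4 is 15 ± 2 = Day 13 to 17; Visit 5 is 30 ± 5 = Day 25 to 35, which is 11 days. Gap between operations (2.3.1): 6 to 15 days. The protocol gives no figure of its own for off-drop observation, so there is none to reproduce.

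**Formula.** Second eye: day of eye = visit day. First eye: day of eye = visit day + gap. Off-drop time = day of eye − day of last drop; a negative value means still on drops.

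| | Day of eye | Off-drop time, last drop Day 28 | Off-drop time, last drop Day 27 |
|---|---|---|---|
| Second eye, Visit 4 | 13 to 17 | −15 to −11 | −14 to −10 |
| Second eye, Visit 5 | 25 to 35 | −3 to 7 | −2 to 8 |
| First eye, Visit 4 | 13 + 6 = 19 to 17 + 15 = 32 | −9 to 4 | −8 to 5 |
| First eye, Visit 5 | 25 + 6 = 31 to 35 + 15 = 50 | 3 to 22 | 4 to 23 |

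**Second eye at Visit 5.** With a Day 28 last drop, Days 25, 26 and 27 precede it and Day 28 coincides with it: 3/11 = 27% of permitted days before, 4/11 = 36% before or on. With a Day 27 last drop the shares are 2/11 = 18% and 3/11 = 27%. At nominal Day 30, off-drop time is 30 − 28 = 2 days.

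**Second eye at Visit 4.** The visit falls from 1 day before (13 − 14) to 3 days after (17 − 14) the end of highest-frequency dosing, and 11 to 15 days before a Day 28 last drop. It cannot show rebound after stopping.

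**First eye.** At Visit 5 it is off drops for every permitted combination of visit day and gap. At Visit 4 it is usually in taper; with a long gap it may already be off drops, by up to 4 days (5 with a Day 27 last drop).

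**Within a subject.** Both eyes are examined at the same visit, so their off-drop times differ by the gap, 6 to 15 days.

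**Course started at Visit 5.** 2 + 7 + 7 = 16 days. Started on Day 25 to 35, its last day is 25 + 15 = 40 to 35 + 15 = 50, counted from second-eye surgery. That is after the final visit whichever eye is treated.

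**The case against.** Several stronger readings are tempting, and the documents do not support them.

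- **That every eye is affected.** The visits run from second-eye surgery, so each first eye is at least 3 days past its last drop at Visit 5. Half of all eyes are examined off drops there.
- **That the comparison of regimens is biased.** Section 3.3.2 balances which group the first eye falls in, so test and control eyes are second-operated about equally often. Detection is lost in both regimens alike, giving fewer events to compare but favouring neither.
- **That an early Visit 5 misses the one step at which the regimens differ.** They differ earlier too: in frequency during the first two weeks, and again in week 4 (once a day against twice a day).
- **That ordinary Day 15 inflammation will be called rebound.** The definition requires symptoms as well as cells or flare, so a slit-lamp finding alone does not meet it. It remains true that the definition does not mention reduction or withdrawal of the steroid, so it should be read against the drop schedules.
- **That the efficacy results are at risk.** Rebound is not among the endpoints in 5.3.1 or 5.3.2.

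Two further objections have some force. The 27 to 36% is a share of permitted days in second eyes, not a forecast of visits. If visits were spread evenly over the window (an assumption), it would be about 14 to 18% of all eyes, and at nominal Day 30 no eye is still on drops. A patient with a painful eye may also return unprompted, but the protocol plans no contact after Visit 5 and records events at study visits, so nothing ensures that such a return enters the data.

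**Conclusion.** The point holds for the second-operated eye and, as regards unrecorded outcomes, for either eye. Rebound in second eyes is assessed before or on the last drop day on up to 4 of 11 permitted days (up to 3 with a Day 27 last drop), and off-drop observation is never longer than 7 to 8 days. Off-drop observation is also unequal within each subject. The consequence is under-detection, so a low rebound count in second eyes would be weak reassurance. It is not evidence of bias between regimens and does not touch a listed endpoint. This is a modest weakness in safety follow-up that wording changes can remove.

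The verdict assumes that each eye's drops run from its own surgery, that first eyes have no Day 15 and Day 30 visits of their own, and that visit timing does not depend on which eye received which regimen. If visits were instead scheduled separately for each eye, which Table 1 and Appendix 1 leave open, the same timing problem would apply to every eye.

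**What to change.** 1. Open the Visit 5 window only after the last scheduled drop in the second eye and keep its upper limit, for example Day 29 to 35. Align 3.3.1, Table 1 and 5.3.1, and also 5.3.2, which gives corneal thickness a Day 30 ± 3 window (Day 27 to 33) that already differs from ± 5. State in Table 1 and Appendix 1 which eye's surgery the days count from. Cost: 11 − 7 = 4 fewer scheduling days, and a slightly narrower window for the Day 30 macular thickness measurement taken at the same visit.
2. Record days since the last steroid drop for each eye at Visits 4 and 5, and report rebound by eye order. Cost: one field per eye per visit and one extra table split.
3. Amend 4.5 so that the outcome of any rebound or ocular adverse event unresolved at Visit 5 is recorded. Cost: a few extra follow-up records.
4. The sponsor should reconcile the rebound definition in 3.3.2 with the drop schedules in 3.2, so that it is clear what an event at Visit 4 or on an early Visit 5 represents. No dose, taper or treatment trigger is proposed here.

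None of this changes the sample size or adds a routine visit.
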